# DIDIT: Diuretic/Cool Dialysate Trial

• uKIM-1								
• uHGF								
• *Urinary microRNA (taken from fresh void)	X					X		

## 13. Data Analysis

For both studies, patient characteristics and outcomes will be summarized by study arm. Primary outcomes include 6-month change in RRF. Differences between baseline and 6 months will be calculated and analyzed with a mixed model that incorporates potentially important covariates, such as age, gender and ethnicity. For measurements that will be taken monthly, such as albumin, a repeated measures analysis of variance also will be conducted on the measurements rather than the differences. If needed, transformations or analyses based on ranks will be utilized. This approach will also be used for other outcomes that can be treated as continuous variables, such as HRQOL, inflammatory markers and the number of days of hospitalization. For discrete variables, such as the number of hospitalizations, either logistic regression or Poisson regression will be used. The time to first hospitalization will be examined using Kaplan-Meier plots. To adjust for study site and baseline covariates, the proportional hazards model will be used. All analyses will be intent-to-treat, in that patients will be included in analyses regardless of whether the intervention was applied as intended. Estimates of mean change will be obtained along with 95% confidence intervals. All analyses will be conducted in SAS.

This pilot study will inform the design of a larger clinical trial. For Specific Aim 2, the proportions recruited and retained will be estimated. With a recruitment and randomization of 20 patients, the proportion retained can be estimated to within  $\pm 0.18$  with a 95% confidence interval. Estimates of mean changes, along with estimates of variability, will be obtained and used in designing the larger clinical trial.

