# DIDIT: Diuretic/Cool Dialysate Trial

No Diuretic (placebo) and 37°C dialysate	No Diuretic (placebo) and 35.5°C dialysate
Diuretic and 37°C dialysate	Diuretic and 35.5°C dialysate

The study sample will be selected using an approach to limit drop-out while enhancing generalizability and the main analysis will be intention-to-treat. *Considering the intervention cannot be double-blinded, we have made efforts to reduce bias by using objective outcomes and blinding the assessment of patient-reported outcomes.* Subjects will be recruited for 18 months. An additional 6 month period will be used to complete the intervention in the last subjects and they will be re-assessed at month 8 for an end of study evaluation. The recruitment and participation parameters for development of this formal RCT will assess whether the large scale study can meet enrollment criteria and target timelines, and whether patients can be maintained on the study protocol without safety concerns.

In this pilot study we will assess as primary patient outcomes:

- The change in RRF over 6 months
- The association of cool dialysis and/or diuretic with inflammation
- The association of cool dialysis and/or diuretic use with acute kidney injury (AKI) biomarkers.

The secondary patient outcomes will be:

- Change in HRQOL
- Time to first-hospitalization.

Being a pilot study, our focus is on assessing whether changes in RRF can be detected with the proposed technique (urinary creatinine and urea clearance). Biomarkers of inflammation and AKI will be collected to supplement the functional measurement of renal filtration and as surrogate biomarkers of benefit or safety (e.g. nephrotoxicity) that can be monitored in the large scale study.

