## 12. Study Procedures

**Table 1: Schedule of the study tests/assessments/intervention during the pre-trial (4 wks), intervention (24 wks or 6 months) and post-trial periods (4 wks).**

		Study Phases →	p r e	intervention						p o s t	Time to do
	Measurements/Tests	Month →	0	1	2	3	4	5	6	7	
Intervention	Randomization Intervention: (to one of the following arms) 

• Cool dialysate and placebo

• Cool Dialysate and Bumetanide (3mg/day)

• Isothermic dialysate and placebo

• Isothermic dialysate and Bumetanide (3mg/day)

		X								
	Issue (Bumetanide or placebo): For participants whose pre-intervention 24-hour urinary Creatinine and Urea clearance results allow them to complete the study, any current diuretic will be discontinued prior to taking the "study drug".			X			X				During Dialysis
	Bumetanide/placebo compliance check						X		X		
Blood tests & HD Rx	Routine: (Obtain from DCI monthly labs) 

• Albumin (g/dL)

• Hemoglobin (g/L)

• Intact parathyroid hormone (pg/ml)

• Kt/V

• Potassium (mEq/L)

• Calcium (mg/dL)

• Sodium (mEq/L)

• BUN (mg/dL)

• Creatinine (mg/dL)

		X	X	X	X	X	X	X	X	Collect with DCI monthly labs if values are older than 30 days
	Additional blood tests: [Total blood: 11ml: 10ml collected; 1ml waste] 

• B2-microglobulin (drawn pre- and post-HD)

• Cystatin

• NGAL

• KIM-1

• CRP (mg/L)

		X		X			X			Collected with DCI monthly labs

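### The repeated-measures ANOVA of monthly labs names no months, contrast or baseline adjustment; an arm effect averaged over all eight scheduled labs would be about 25% too small

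*Combined protocol and SAP*

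**What the plan says.** Section 13 gives two analyses for continuous outcomes. The first uses change scores: "Differences between baseline and 6 months will be calculated and analyzed with a mixed model". Age, gender and ethnicity are its example covariates. The second is for outcomes measured every month, with albumin as the named example. For these, Section 13 plans the following: "a repeated measures analysis of variance also will be conducted on the measurements rather than the differences". The word also makes it an addition to the change analysis. On reporting, the section says: "Estimates of mean change will be obtained along with 95% confidence intervals".

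Table 1 in Section 12 covers "pre-trial (4 wks), intervention (24 wks or 6 months) and post-trial periods (4 wks". Its row beginning "Routine: (Obtain from DCI monthly labs" is marked in all eight columns: month 0, months 1 to 6 and month 7. The row includes albumin, hemoglobin, Kt/V, potassium, calcium, sodium, BUN and creatinine.

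For the repeated-measures ANOVA, Section 13 does not state:
- which of the eight months are outcomes;
- whether month 0 is an outcome or a covariate;
- what happens to month 7;
- whether the test is the arm main effect or the arm-by-month interaction.

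The section attaches adjustment for baseline covariates explicitly only to the proportional hazards model.

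**The concern.** Month 0 comes before treatment, so randomization makes its expected arm difference zero. Month 7 falls in the post-trial period, so its arm difference is whatever carries over. A main effect averaged over all eight labs mixes six treated months with two untreated ones and estimates less than the on-treatment difference.

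The lack of baseline adjustment is a separate loss. The arm main effect on raw values is tested against between-patient variation. A patient whose albumin is always low adds noise to it, although the month 0 value that would remove much of that noise is already collected.

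At stake is the quality of the monthly lab estimates from a pilot of 20 patients. Section 13 says that its estimates of change and variability will be used to design the larger trial. Leaving the contrast open also allows it to be chosen after the data are seen.

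**Working it through.** The plan gives no effect size, SD, correlation or power for the labs, so there is no stated figure to reproduce.

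**Inputs from the documents.** Eight scheduled labs, six in the intervention period (Table 1); 20 patients (Section 13); two factors in a two-by-two design (Section 3).

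**Assumptions.** Balanced allocation, so 10 v 10 for each factor; SD 1 in every month; compound symmetry with within-patient correlation ρ = 0.6; effect d = 0.8 SD, constant in months 1-6 and zero at months 0 and 7; two-sided 5%; complete data. The second factor is ignored in the error degrees of freedom, as is chance imbalance in the covariate.

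**Step 1: dilution.** Equal-weight average over months 0-7, by pattern of effect:

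| Pattern | Average over 8 labs | Shortfall from d |
|---|---|---|
| None at months 0 and 7 | 6d/8 = 0.75d | 25% |
| Half carry-over at month 7 | 6.5d/8 = 0.8125d | 18.75% |
| Full carry-over at month 7 | 7d/8 = 0.875d | 12.5% |
| Month 1 lab drawn before first dose, none at month 7 | 5d/8 = 0.625d | 37.5% |

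The last row is possible because Table 1 marks the first drug issue at month 1. In that case the months 1-6 average is itself only 5d/6.

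**Step 2: variance per patient.** The mean of m months has variance ρ + (1 − ρ)/m.
- Eight months: 0.6 + 0.4/8 = 0.650
- Months 1-6: 0.6 + 0.4/6 = 0.667
- Months 1-6 given month 0: 0.667 − 0.6² = 0.307

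Including months 0 and 7 does not widen the interval (0.650 v 0.667). They shrink the estimate; the missing covariate is what costs precision. The standard error of the 10 v 10 difference is √(0.2 × variance): 0.361, 0.365 and 0.248 respectively.

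**Step 3: power from the noncentral F.** For a main effect, the noncentrality is 5 × effect²/variance, where 5 = 10 × 10/20.

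| Analysis | Noncentrality | df | Power |
|---|---|---|---|
| Main effect, 8 months | 5 × 0.60²/0.650 = 2.77 | 1, 18 | about 35% |
| Main effect, months 1-6 | 5 × 0.80²/0.667 = 4.80 | 1, 18 | about 55% |
| Arm-by-month, 8 months | 5 × 0.96/0.4 = 12.0 | 7, 126 | about 68% |
| Months 1-6, month 0 as covariate | 5 × 0.80²/0.307 = 10.4 | 1, 17 | about 86% |
| Change, month 6 minus month 0 | 5 × 0.80²/0.8 = 4.0 | 1, 18 | about 47% |

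In the arm-by-month row, 0.96 is the sum of squared deviations of the monthly effects from their mean of 0.60: 2 × 0.60² + 6 × 0.20². The divisor 0.4 is 1 − ρ. In the change row, 0.8 is 2(1 − ρ).

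**Step 4: sensitivity.** Arm-by-month against months 1-6 with covariate gives 48% v 82% at ρ = 0.4 and 96% v 97% at ρ = 0.8. Against the eight-month main effect, effect/SE with the covariate is 1.6 to 2.8 times larger for ρ = 0.4 to 0.8. Under AR(1) with ρ = 0.6 to 0.9 it is 1.3 to 2.0 times larger; at AR(1) 0.8, power is 37% v 72%.

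**The case against.** The strongest objection is that the plan never says months 0 and 7 are averaged into an arm effect. A reader might infer that they are, because Table 1 marks them and Section 13 sets no window. But Table 1 is a collection schedule, not a definition of the analysis set. In a repeated-measures ANOVA with a pre-treatment value, the arm-by-month term is at least as natural a test. Month 0 then belongs in the response, the effect is not diluted, and stable between-patient differences drop out of the error. This stands, and it makes the 25% conditional. The interaction still spreads the effect over 7 degrees of freedom and yields no single on-treatment difference with an interval.

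Second, the change analysis already compares arms on treatment relative to baseline and excludes month 7. That also stands: the plan does not rest on the ANOVA alone. But the change score uses two of the eight labs, and the ANOVA is there to use the rest.

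Third, this is a feasibility pilot, the routine labs are not among the patient outcomes listed in Section 3, and no power target is set for them. That limits the importance. The power figures are a way to rank the options, not a target the trial has missed.

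**Conclusion.** The point holds conditionally. Section 13 leaves the months, the contrast and the role of the baseline value undefined. If the arm main effect over all eight labs is used, it understates a constant on-treatment difference by about 25% with no carry-over and by 12.5% with full carry-over at month 7. It also carries between-patient noise that the month 0 value could remove.

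Three stronger readings are not supported:
- **A quarter as the ceiling.** The shortfall is 37.5% of the full effect if the month 1 lab precedes the first dose.
- **The whole gain from 35% to 86% as the cost of months 0 and 7.** Restricting the window moves power from about 35% to about 55%, roughly 19 points before rounding; the rest comes from baseline adjustment.
- **A threat to the main result.** The primary outcome "The change in RRF over 6 months" comes from 24-hour urine collections and does not use this ANOVA.

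The correlations, the effect size and the constant effect are assumptions. The advantage of months 1-6 with the covariate over the eight-month main effect held at every correlation examined. Its advantage over arm-by-month nearly vanishes at ρ = 0.8. This is a nearly free improvement to a supplementary analysis.

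**What to change.** Replace the repeated-measures sentence in Section 13 with wording to this effect: monthly laboratory values from months 1 to 6 are the outcomes in a repeated-measures model; the month 0 value of the same laboratory test is a covariate; the average on-treatment difference is reported for each factor (bumetanide v placebo, 35.5 °C v 37 °C) with a 95% confidence interval; month 7 is summarised separately as an off-treatment value. State also whether the month 1 lab is drawn after the first dose, since that decides whether it is an on-treatment value. An arm-by-month plot or test can be kept as a description of timing.

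Moving to a mixed model on the same eight months, with nothing else changed, would not settle the matter: the window, the contrast and the baseline handling would still be open.

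The cost is a few lines of text and one degree of freedom for the covariate. No new data or visits are needed, and month 7 is still reported.

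### The planned repeated measures ANOVA, if fitted classically, and the RRF change-score analysis both lose patients with missing visits; a mixed model on all measurements would keep them

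*Combined protocol and SAP*

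**What the plan says.** All of this is in Section 13 (Data Analysis) of the combined protocol and SAP.

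- For the 6-month change in RRF: "Differences between baseline and 6 months will be calculated and analyzed with a mixed model", with age, gender and ethnicity given as examples of covariates.
- The next sentence adds a second method. "For measurements that will be taken monthly, such as albumin", the plan says that "a repeated measures analysis of variance also will be conducted on the measurements rather than the differences".
- After a sentence on transformations and ranks, it continues: "This approach will also be used for other outcomes that can be treated as continuous variables, such as HRQOL, inflammatory markers". It does not say whether the approach meant is the mixed model on differences, the ANOVA, or both.
- On the analysis population: "All analyses will be intent-to-treat, in that patients will be included in analyses regardless of whether the intervention was applied as intended".
- On software: "All analyses will be conducted in SAS". No procedure, estimation method, covariance structure or treatment of missed visits is given here or elsewhere in the document.

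**The concern.** The plan names a mixed model in one sentence and a repeated measures ANOVA in the next, so the natural reading is that these are two methods and that the second is the classical one. Classical repeated measures ANOVA works on complete rows: one missing visit removes the patient. A likelihood-based mixed model fitted to the same measurements does not do this.

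Missing visits are foreseeable. The Background section cites annualized mortality of 35-40% in the first six months of dialysis. Section 15 allows withdrawal at any time and ends study treatment on transplantation, home dialysis or transfer elsewhere. Section 4 tolerates limited absences and does not count hospital stays as unavailability.

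With about 20 patients in four factorial cells, each loss matters. If the patients lost are those who died, transferred or were in hospital, those analyzed may be healthier than those randomized. Section 13 says that the mean changes and their variability will be used to design the larger trial, so selective loss could carry forward into that design.

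**Working it through.** **The plan's own figure.** The only precision statement is ±0.18 for the proportion retained with 20 patients. The Wald half-width is 1.96 × √(p(1−p)/n). With n = 20 and p = 0.80 (p is not stated), it is 1.96 × √(0.16/20) = 0.175, which rounds to 0.18. At p = 0.75 it is 0.190 and at p = 0.85 it is 0.157. The figure reproduces, and it fits planned retention near 80%, which is used below as an assumption.

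**Inputs.**
- n = 20 (Section 13). Section 7 says 25 randomized and Section 5 says 20 followed to completion; the fractions below apply to any n.
- K = 8 time points for routine labs, months 0 to 7 (Section 12, Table 1), or 7 without the post-trial month.
- K = 3 for RRF, inflammatory markers and questionnaires (Table 1). The Section 23 compensation table likewise lists three urine collections and three questionnaire sessions.
- m = missed-visit rate. The documents give none, so 2%, 5% and 10% are assumed, independent across visits.

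**Classical ANOVA.** Expected complete patients = n × (1−m)^K.

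| K | m = 2% | m = 5% | m = 10% |
|---|---|---|---|
| 8 | 20 × 0.851 = 17.0 | 20 × 0.663 = 13.3 | 20 × 0.430 = 8.6 |
| 7 | 20 × 0.868 = 17.4 | 20 × 0.698 = 14.0 | 20 × 0.478 = 9.6 |
| 3 | 20 × 0.941 = 18.8 | 20 × 0.857 = 17.1 | 20 × 0.729 = 14.6 |

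Equal allocation gives 5 patients per cell. At K = 8 that falls to about 4.3, 3.3 and 2.2 (17.0, 13.3 and 8.6 divided by 4).

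If 80% are retained and the rest lost, 16 of 20 remain with no other gaps. With a further 5% missed per visit among those retained, 16 × 0.663 = 10.6 remain over eight visits.

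**Simulation check (K = 8, m = 5%).** Over 2,000 simulated patterns the mean number of complete patients was 13.3, with a 95% range of 9 to 17. In one simulated dataset 12 patients were complete, while a mixed model on the measurements used all 20 (151 of 160 observations).

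**Change score for RRF.** Each patient yields one baseline-to-6-month difference. With no 6-month value there is no difference, and calling the model mixed does not help, because it has no other value from that patient. At 80% retention, 20 × 0.80 = 16 remain; at 90%, 18.

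**Is 80% retention implausible?** Reading 35-40% as a yearly rate, six-month mortality is 1 − exp(−0.175) = 16% to 1 − exp(−0.20) = 18%. Reading it as a yearly risk, it is 1 − √0.65 = 19% to 1 − √0.60 = 23%. That is about 3 to 5 of 20. It is an upper guide only: Section 4 excludes life expectancy under six months, and its inclusion criteria do not require recent dialysis start.

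**The case against.** Four objections have force.

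1. **Deletion is not certain.** Repeated measures ANOVA can be run in SAS classically or in a mixed-model procedure that uses all visits. The plan does not say which, so a statement that patients will be dropped goes beyond the text. This stands, and the loss is conditional on a classical fit.

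2. **There is no contradiction with intent-to-treat.** A reader might infer that deletion breaks the plan's own rule. The rule is defined by whether the intervention was applied as intended. It concerns adherence and is silent on incomplete data. Deletion runs against the usual aim of analyzing everyone randomized, but the documents do not contradict themselves.

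3. **Scope is limited.** The ANOVA is additional and tied to monthly measurements. Its example, albumin, is neither a primary nor a secondary outcome in Section 3. Inflammatory markers (primary) and HRQOL (secondary) are measured three times, so they come under it only through an ambiguous phrase. It is tempting to say that a primary outcome will be analyzed this way; the text allows that but does not establish it.

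4. **The size is assumed.** Routine labs come from clinic records and may be nearly complete. Independent gaps are also an adverse assumption: if the same few patients miss most of the visits, fewer patients are deleted at the same overall rate.

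Section 5 might also seem to answer the RRF point, since recruitment continues until 20 patients complete. That protects the number but not the selection: at 80% retention, 20/0.80 = 25 would be randomized and the 5 non-completers would have no change score.

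**Conclusion.** The point holds in conditional form. Read naturally, the plan uses classical ANOVA for serial measurements, and at assumed missed-visit rates of 5-10% that would discard roughly a third to over half of 20 patients over eight monthly visits, or about 3 to 5 of 20 over three visits. At 2% the loss is small: about 3 patients and 1 patient respectively.

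The RRF weakness does not depend on which SAS procedure is used. It follows from analyzing a single difference per patient and touches the named primary outcome; at an assumed 80% retention it costs 4 of 20.

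Loss of precision is certain wherever patients are deleted. Bias is possible, not shown: it arises if the patients lost differ in their course from those kept, and the documents give no data on that. The planning inputs are mean changes and their variability, which come most directly from the difference analysis, so the risk to the larger trial's design runs chiefly through that analysis and less through the supplementary ANOVA on monthly labs.

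**What to change.** Replace the repeated measures ANOVA, and the difference analysis for RRF, HRQOL and inflammatory markers, with one method. Suggested wording:

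> *Serial continuous outcomes will be analyzed with a likelihood-based linear mixed model for repeated measures (REML, Kenward-Roger degrees of freedom), fitted to all available measurements from all randomized patients. Baseline is one of the repeated outcomes. Fixed effects are the two treatment factors, visit, each factor-by-visit interaction, age, gender and ethnicity. Within-patient covariance is first-order autoregressive. The 6-month change, and its difference between levels of each factor, are reported as model contrasts with 95% confidence intervals. Data are assumed missing at random; deaths are reported by arm alongside.*

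Three details matter.

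- **Baseline as an outcome.** As a covariate it would still exclude anyone with no post-baseline value. Section 4 makes the first urine collection a condition of randomization, so every randomized patient should have a baseline RRF and enter the model. A patient with only that value adds little about change; the main gain is from patients with an intermediate value.
- **One covariance structure, fixed in advance.** First-order autoregressive is an example. Leaving a choice of structures open would defeat the purpose with so few patients.
- **RRF included by name.** Otherwise the repair reaches a supplementary analysis and misses the primary one.

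The cost is plan wording: same data, same software, no new visits. The downsides are reliance on missing-at-random and on a simple covariance structure. The model also does not define values after death, which is why deaths need separate reporting. A short sensitivity analysis of the missing-at-random assumption would be a reasonable addition.

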### **3. Study Design**

This pilot RCT will demonstrate the feasibility and safety of performing a large scale study of diuretic use and/or cool dialysate by examining recruitment, retention, and key outcomes. This study will further assess whether the use of a diuretic compared to non-use of a diuretic (placebo) and/or the use of cool dialysate (35.5 °C) compared to 37 °C for up to 6 months will improve RRF, improve HRQOL and reduce hospitalizations. by randomizing 20 chronic hemodialysis patients from DCI centers in the greater Albuquerque area, to either bumetanide and cool dialysate randomized in a two-by-two factorial distribution.

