## 7. Study Endpoints

# DIDIT: Diuretic/Cool Dialysate Trial

- Recruit and randomize 25 incident chronic in-center HD patients with urine output >200 mL/day and to 3 mg of oral bumetanide once daily and/or to cool dialysate (35.5 °C).
- Estimate recruitment and retention rates anticipated in a full-scale study.
- Compare changes in RRF markers between groups.
- Collect preliminary data on adverse events (AE) and serious adverse events (SAE), biomarkers of inflammation and injury to native kidneys, HRQOL, health care utilization and other potential outcomes of a full-scale trial.

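### The measurement scale for the inflammatory and kidney-injury markers is not fixed in advance, and the marker's own baseline is not named as a covariate

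*Combined protocol and SAP*

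**What the plan says.** Section 3 (Study Design) lists three primary patient outcomes: change in residual renal function (RRF), "The association of cool dialysis and/or diuretic with inflammation", and the corresponding association with acute kidney injury (AKI) biomarkers. Table 1 in Section 12 lists the assays, among them CRP, IL-6, TNF-α, IL-1β, NGAL, KIM-1 and cystatin in blood, and NGAL, KIM-1, HGF and cystatin C in urine.

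Section 13 (Data Analysis) sets the method, first for residual function: "Differences between baseline and 6 months will be calculated and analyzed with a mixed model that incorporates potentially important covariates, such as age, gender and", the list closing with ethnicity. On scale it adds "If needed, transformations or analyses based on ranks will be utilized". It then carries the method over: "This approach will also be used for other outcomes that can be treated as continuous variables, such as HRQOL, inflammatory markers", with days of hospitalization as a further example. AKI markers are not named anywhere in Section 13, although the list of other outcomes is given by example and could be read to include them.

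The same section promises mean changes with 95% intervals, and says that these and the estimated variability will feed the design of the larger trial.

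**The concern.** Marker concentrations are positive and may well be right-skewed. If they are, a few high values dominate an untransformed difference, and the comparison between arms becomes imprecise. The plan allows a transformation but does not say which one, what would prompt it, or when the decision is made. With about 20 patients, a normality check will often miss real skewness.

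Three things are at stake: the precision of two of the three primary patient outcomes, whether the reader can be sure that the reported scale was not one of several tried, and whether the SD passed to the larger trial is stable enough to plan with. A rank analysis, one of the two permitted fallbacks, yields no mean change or SD for planning.

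**Working it through.** **The plan's own figure.** The only design calculation is the precision of the retention proportion, ±0.18 with 20 patients. The half-width is 1.96·√(p(1−p)/20). At p = 0.80 it is 0.175, at p = 0.785 it is 0.180, and at p = 0.50 it is 0.219. The figure reproduces at an assumed retention of about 0.8. It says nothing about markers.

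**Inputs from the documents.**
- Sample size: "With a recruitment and randomization of 20 patients" (Section 13). Section 7 has a different number, "Recruit and randomize 25 incident chronic in-center HD patients". That conflict is a separate matter, and 20 is used here.
- Design: "randomized in a two-by-two factorial distribution" (Section 3). No ratio is stated. With equal allocation, each main effect compares 10 v 10.
- Level: two-sided 0.05, inferred from the 95% intervals.

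**Inputs assumed, because the documents give none.** Lognormal markers, log-SD σ from 0.3 to 1.2, log correlation ρ between baseline and 6 months of 0.5 to 0.7, and a multiplicative treatment effect.

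**Method.** 20,000 simulated trials per setting (4,000 for the normality-driven rule), comparing two groups by t test on each scale. The effect is set so that a pre-set log-change analysis has 80% power. The SD of log change is σ√(2(1−ρ)), and a 10 v 10 t test needs a standardized difference of about 1.32. For σ = 0.8 and ρ = 0.5 the SD is 0.8 × √1.0 = 0.80, so the ratio is exp(−1.32 × 0.80) = 0.35. For ρ = 0.7 the SD is 0.8 × √0.6 = 0.62, so the ratio is exp(−1.32 × 0.62) = 0.44.

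**Power of the untransformed change where log change has 0.80.**

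| Log-SD | Power, untransformed change | Relative loss |
|---|---|---|
| 0.3 | 0.67-0.69 | about 15% |
| 0.5 | 0.56-0.59 | about 28% |
| 0.8 | 0.39-0.41 | about 50% |
| 1.0 | 0.30-0.32 | about 61% |
| 1.2 | 0.23-0.24 | about 70% |

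For example, at 0.8: (0.80 − 0.40)/0.80 = 50%.

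**Other uses of the clause, same settings.**
- Ranking the untransformed differences gives 0.50-0.54 at log-SD 0.8 and 0.42-0.45 at 1.2. At 0.8 this recovers (0.50 − 0.39)/(0.80 − 0.39) = 27% to (0.54 − 0.41)/(0.80 − 0.41) = 33% of the gap.
- Switching to logs when a Shapiro-Wilk check fails gives 0.64-0.71, a loss of (0.80 − 0.71)/0.80 = 11% to (0.80 − 0.64)/0.80 = 20%. A switch to ranks instead does no better than ranks do in general.
- A log analysis with the log baseline as covariate gives 0.83-0.88, better than log change itself.

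**A fixed effect, for scale.** With a true halving and ρ = 0.6, power at log-SD 0.8 is 27% for untransformed change, 32% for ranks of it (Mann-Whitney), 53% for log change and 60% for log values adjusted for log baseline. At log-SD 1.0 the figures are 17%, 23%, 38% and 42%.

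**Type I error per marker.** Untransformed change 2.8-4.8%, normality-driven choice 4.8-5.8%, smallest p-value of untransformed, log and rank 6.6-8.2%.

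**Stability of the planning variance.** Required sample size is proportional to the variance. With no effect, the ratio of the 95th to the 5th percentile of the estimated variance is about 11 for untransformed change and 3 for log change at log-SD 0.8. At 1.0 it is about 19 against 3.

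**The case against.** The strongest reply is that Section 13 already permits the remedy. It never says that differences stay untransformed, and its clause allows logs. This stands: the larger losses in the table occur only if the clause is not used.

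A reader might also infer that the scale will be chosen from unblinded data, and that the plan therefore both halves power and inflates error. The documents do not support this. They are silent on when the choice is made. The halving needs a log-SD near 0.8, which the documents do not give. The inflation needs selection by p-value, which they do not describe. The two harms also come from different uses of the clause: one from leaving the scale alone, the other from trying several scales and keeping the best.

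Third, this is a feasibility pilot of about 20 patients with no stated marker test, power or go/no-go rule, so no declared decision depends on these error rates. That limits the weight of the point, and power is best read here as a measure of precision. It does not remove the planning argument, because estimating variability for the next trial is a stated purpose. SDs can be recomputed later on any scale, but the plan does not say which one will be reported.

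Finally, the simulation assumes lognormal data and a multiplicative effect, which favors logs, and uses two-group tests in place of the planned covariate-adjusted mixed model. The covariate list is given by example, so baseline is not ruled out. These are fair limits on the size, not on the gap in the text.

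**Conclusion.** The point holds as one of pre-specification and efficiency. For two of the three primary patient outcomes, the plan does not settle the scale, the rule for changing it, or adjustment for the marker's baseline, and Section 13 does not name the AKI markers at all.

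The size depends on skewness that the documents do not report. Under the stated assumptions the loss of power is about 15% to 70% if untransformed differences are kept and about 11% to 20% with a normality-driven switch to logs. Ranking the differences recovers only about a third of the gap or less at log-SD 0.8. The claim that half the power is lost is one point in that range and should not be quoted alone. No single method inflates Type I error, and neither does a normality-driven choice. The rise to about 7-8% per marker is a risk that the open wording leaves possible, not something the plan sets out to do.

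This is a cheap improvement and not a flaw that threatens the pilot.

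**What to change.** Keep the existing sentence in Section 13 for the other outcomes. Days of hospitalization, for example, can be zero and may still need a transformation or ranks. Then add:

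> Blood and urine concentrations of inflammatory and kidney-injury markers will be analyzed on the natural-log scale, with the log baseline value as covariate and the two randomized factors as terms, and reported as geometric mean ratios with 95% confidence intervals and the log-scale SD. Values below the detection limit will be handled by a rule fixed before unblinding. Rank-based analysis is a sensitivity analysis only.

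Section 3 states that the intervention cannot be double-blinded, so in practice the detection-limit rule should be written down before anyone sees marker results by arm. MicroRNA and spot urine creatinine are outside this wording and need their own line if they are to be analyzed.

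The cost is a few sentences and one decision on undetectable values. No new samples, visits or patients are needed, since the baseline markers are already in Table 1. The small downside is that results come out as ratios and not as mean changes in original units. The latter can still be tabulated descriptively, which keeps the promise of mean changes in Section 13.
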